	
shortest dosing schedule for primary vaccination series in the participated databases (SIDIAP in Spain)
 
 whether the vaccination record is 1st, 2nd, 3rd or 4th dose. 
Objective 4: Persons requiring intensive services during a hospitalisation with COVID-19 during the Omicron period will have:
 
 intensive services initiated during a hospitalisation. 
Objective 5: same as objective 1-4

Exposure:	
Objective 1: N/A
 
Objective 2: SARS-CoV-2 infection
 
Objective 3: Vaccination against SARS-CoV2 infection
 
Objective 4: Incidence VTE or ATE, or worsening severity after SARS-CoV2 infection
 
Objective 5: SARS-CoV2 infection and Covid-19 vaccines

Comparator:	
Objective 1 – 3 are descriptive incidence rate, not applicable.
 
Objective 4: No incidence VTE or ATE, or worsening severity after SARS-CoV2 infection
 
Objective 5: background population

Outcome:	
1. Venous thromboembolic events
 
In the primary analysis, venous thromboembolic events will be identified by diagnostic codes for pulmonary embolism or deep vein thrombosis.
 
2. Arterial thromboembolic events
 
In the primary analysis, arterial thromboembolic events will be identified by diagnostic codes for an acute myocardial infarction or acute ischemic stroke.

Time (when follow up begins and ends):	
Objective 1: follow-up will begin on January 1st 2017 or 365 days of prior history and continue up until the first of: outcome of interest, loss to follow-up, death or December 31st 2019.
 
Objective 2: follow-up will begin on their index date and continue up until the first of: outcome of interest, loss to follow-up, death, or either 30-, 60-, 90- or 180-days after the index date (depending upon the follow-up time period of interest).
 
Objective 3: follow-up will begin on their index date and continue up until the first of: outcome of interest, loss to follow-up, death, or

	Phase II C3-001 – Study Protocol	
	Author(s): [name], [name]	Version: v3.1
	Dissemination level: public	

	either 30-, 60-, 90- or 180-days after the index date (depending upon the follow-up time period of interest).
Setting:	Inpatient and outpatient setting using data from the following datasources: IPCI (NL), SIDIAP (Spain), IQVIA Germany (Germany), Estonian Biobank – via Utartu (Estonia) and CPRD GOLD (UK). Inpatient information is only available in SIDIAP.

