8.3 Study Period

The study period will start depending upon when the Omicron variant became established in Europe commencing from 1st December 2021.[8] The end of the study period will be the last available date of data collection for each contributing dataset.

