8.4 Follow-up

For cohort 1, follow-up will begin on January 1st 2017 and continue up until the first of: outcome of interest, loss to follow-up, death or December 31st 2019. For cohorts 2 to 5, follow-up will begin on their index date and continue up until the first of: outcome of interest, end of observation period, end of data availability, death, or either 30-, 60-, 90- or 180-days after the index date (depending upon the follow-up time period of interest).

Table 2: Operational Definition of Time 0 (index date) and other primary time anchors

Study population name(s)	Time Anchor Description (e.g. time 0)	Number of entries	Type of entry	Washout window	Care Setting ¹	Code Type	Diagnosis position	Incident with respect to...	Measurement characteristics / validation	Source of algorithm
Background population (cohort 1*)	January 1 st 2017 or after when they have 365 days of prior history	Multiple	General population	n/a	n/a	n/a	n/a	n/a	n/a	n/a
SARS-CoV-2 infection cohort (cohort 2*)	Date of test for the positive test result for SARS-CoV-2, or date of clinical diagnosis of COVID-19	Multiple	incident	No covid-19 infection within 3 months prior	OP	SNOMED codes (see appendix)				
hospitalised with COVID-19 cohort (cohort 3*)	Date the date of hospital admission	Multiple	incident	No hospitalization within	IP	SNOMED codes (see appendix)				

This document represents the views of the DARWIN EU® Coordination Centre only and cannot be interpreted as reflecting those of the European Medicines Agency or the European Medicines Regulatory Network.

	Phase II C3-001 – Study Protocol	
	Author(s): [name], [name]	Version: v3.1
	Dissemination level: public	

				3 month s prior						
Intensive care service cohort (cohort 4*)	Date of the following depends on availability in data, descend priority: 1.)Date of intensive care service (mechanical ventilation, tracheostomy, or extracorporeal membrane oxygenation (ECMO)); 2.)Date of ICU admission; 3.)Date of hospital admission.	Multiple	incident	n/a	IP	SNOMED (see appendix)	n/a	Covid-19 hospitalized	n/a	n/a
Vaccinated cohort (cohort 5*)	date of vaccination record	Multiple	n/a	21 days	OP	RxNorm codes (see appendix)				

*Cohorts number as described in 8.5 study population with inclusion and exclusion criteria.

¹ IP = inpatient, OP = outpatient, ED = emergency department, OT = other, n/a = not applicable

Description of the different items from the table can be found below:

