8.5 Study Population with inclusion and exclusion criteria

Five non-mutually exclusive study cohorts for the analyses will be defined:

- 1. General population cohort for pre-pandemic background rates** will have
 - Individuals will start contributing as of 1st January 2017, or when they have at least 365 days of data availability.
 - follow-up for this cohort will run up to 31 December 2019.
- 2. Persons tested positive for SARS-CoV-2 or with a clinical diagnosis of COVID-19 during the Omicron period** will
 - have either a positive test result for SARS-CoV-2 or a clinical diagnosis of COVID-19 on or after 1st December 2021 (with the index date being whichever date comes first if both occur)
 - have no positive test result for SARS-CoV-2 or clinical diagnosis of COVID-19 within 3 months prior to the index date.
 - have at least 365 days of data availability prior to index date
- 3. Persons hospitalised with COVID-19 during the Omicron period** will have
 - a hospitalisation on or after 1st December 2021 (with the index date the date of hospital admission),
 - a record of a clinical diagnosis of COVID-19 or a positive test result for SARS-CoV-2 in the period between 3 weeks prior to and up to 3 days following the index date.
 - have no diagnosis of COVID-19 or a positive test result for SARS-CoV-2 between 3 months and 3 weeks prior to index date.
 - have no COVID-19 hospitalisation within 3 weeks prior to the index date.
 - have at least 365 days of data availability prior to index date
- 4. Persons requiring intensive services during a hospitalisation with COVID-19 during the Omicron period** will have
 - intensive services initiated during a hospitalisation as described in cohort 3 (with the index date the date at which intensive services were initiated)
 - patients will have had a confirmatory diagnosis or test result of COVID-19 (both as defined above) within a time window from 3 weeks to their index date up to three days following their index date.
 - have at least 365 days of data availability prior to index date
- 5. Persons vaccinated against SARS-CoV2 infection**
 - a vaccination record identified by brand (with the index date the date of vaccination record)

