8.8.2 Incidence of study outcomes

The incidence of each study outcome described in section 8.6.2 will be estimated during 30-, 60-, and 90- and 180-days following the index date for each cohort of interest with 95% confidence intervals in each database. The 90-day cumulative incidence of study outcomes will be estimated. Given the risk of mortality among patients with COVID-19, particularly among those hospitalised, the competing risk of mortality will be accounted for by estimating cumulative incidence functions. If death is not available, cumulative incidence will be estimated using the Kaplan-Meier approach. As well as estimating the incidence of outcomes for each study cohort as a whole, incidence will also be estimated by age group stratified by sex. Other stratifications by prior COVID-19 diagnosis, prior SARS-CoV-2 vaccination, whether patients were hospitalised on the index date or where immunocompromised on the index date will also be performed.

8.8.3 Assessing the association between risk factors for thromboembolic events and COVID-19 during the Omicron period

To assess the association between potential risk factors on the incidence of venous and arterial thromboembolic events among patients with COVID-19 during the Omicron period, cause-specific Cox models will be used to calculate hazard ratios for the incidence of venous and arterial thromboembolic events for each of the COVID-19 cohorts. Adjusted models will evaluate potential predictors including age, sex, prior COVID-19 infection status, prior vaccination status, cancer, whether patients were immunocompromised on the index date, prior use of antithrombotics, prior use of corticosteroids, and pre-index comorbidities listed in section 8.6.3.

8.8.4 Risks of COVID-19 “worsening” (hospital admission or death) stratified by thromboembolic event occurrence during the Omicron period

[This analysis will only be conducted in the SIDIAP data given the availability of hospital data]

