Model(s): (provide details or code)	Objective 1 -3: We will use Poisson models to estimate incidence rates and 95% confidence interval. Overall, age group, and sex specific rates will be reported. Within each age-sex strata, rates by prior COVID-19 diagnosis, prior vaccination status and brand, and whether patients are immunosuppressed will be reported as well when event number is larger than 5 within the strata. Objective 4a: To assess the association between potential risk factors on the incidence of venous and arterial thromboembolic events among patients with COVID-19 during the Omicron period, cause-specific Cox models will be used to calculate hazard ratios for the incidence of venous and arterial thromboembolic events for each of the COVID-19 cohorts. Adjusted models will evaluate potential predictors including age, sex, prior COVID-19 infection status, prior vaccination status and brand, cancer, whether patients were immunocompromised on the index date, prior use of antithrombotics, prior use of corticosteroids, and pre-index comorbidities. Objective 4b: Cause-specific Cox models within the multistate framework will be used to estimate hazard ratios associated with the risk factors of interest. This approach will allow for the factors of interest to have a different effect by the transition of interest and, where the model includes a state representing deaths, will account for the competing risk of mortality. Models will be adjusted for age and sex. Objective 5: We will calculate crude incidence rate ratios (IRRs) for each event with 95% confidence intervals, for the vaccinated and COVID-19 cohorts compared against the background general population cohort. This will be

	Phase II C3-001 – Study Protocol	
	Author(s): [name], [name]	Version: v3.1
		Dissemination level: public

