8.9 Evidence synthesis

We will pool the results across databases using random effect meta-analyses, I^2 for heterogeneity will be reported.

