The included databases will vary in the data elements that they capture and in their current duration of follow-up. Depending on the dataset, not all study populations will be observed. For example, identifying the intensive services cohort will not be possible where inpatient hospital interventions are not observed. Similarly, not all outcomes may be available in all databases e.g. deaths. Some datasets may not capture COVID-19 diagnoses or tests occurring outside of hospital. Only the cohorts and outcomes that can reliably be identified will be assessed in the analyses. Since the vaccination programs changed over time (e.g. the primary vaccine courses targeted the general population, while the 4th dose were offered to more vulnerable people), the characteristics of patients receiving different doses may differ. However, we will stratify our analysis by prior vaccines whenever the power allows. It will also be assumed that vaccination recording is complete. Due to the availability of more recent data (CPRD is available until July 2022), some databases may have relative short follow-up time for study cohorts, and therefore may impact on the 90-days and 180-days incidence rates. The data elements that each data partner can provide will be detailed. The contextualisation of incidence rates using a historical background period assumes that coding practices and data recording are similar over time. However, this method has been used in previous studies focused on the 1st wave of covid, conducted by the same research group. [20,21] The analysis will calculate crude incidence rates and standardised incidence rates accounting for age and sex only. Differences in other potential confounders factors may exist and the characteristics of each cohort and stratification group will be inspected. No validation of outcomes using case note review will be performed.

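### On the listed SIDIAP lock almost no COVID-19 entry can complete 180 days, so the 180-day rate and SIR are computable but may be weighted to the early days and not comparable across databases before pooling

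*Protocol*

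**What the plan says.** - **Windows.** Section 8.8.2: incidence "will be estimated during 30-, 60-, and 90- and 180-days following the index date for each cohort of interest", in each database. Objective 5 builds its rate ratios from these rates.
- **Entry.** Section 8.5: people in cohort 2 "have either a positive test result for SARS-CoV-2 or a clinical diagnosis of COVID-19 on or after 1st December 2021". Cohort 3 uses the same opening date and cohort 4 arises within cohort 3. No last index date is set. Section 8.3: "The end of the study period will be the last available date of data collection for each contributing dataset".
- **Censoring.** Section 8.4 stops follow-up at the first of several events, among them "end of data availability, death, or either 30-, 60-, 90- or 180-days after the index date".
- **Rates and pooling.** Table 8: "We will use Poisson models to estimate incidence rates and 95% confidence interval". Section 8.9: "We will pool the results across databases using random effect meta-analyses".
- **Locks.** Table 1 lists the last update as 1/6/2022 for SIDIAP, 07/2022 for CPRD GOLD, 1/9/2022 for IQVIA Germany and 1/12/2022 for IPCI. Section 7 (Setting): "Inpatient information is only available in SIDIAP".
- **Limitation.** Section 11 says "some databases may have relative short follow-up time for study cohorts, and therefore may impact on the 90-days and 180-days incidence rates". Its only named example is CPRD, to July 2022.

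**The concern.** An events-per-person-time rate is unaffected by administrative truncation only if the rate is constant after index. Section 6 gives reason to expect a decline: it cites raised DVT risk to 70 days, raised pulmonary embolism risk to 110 days, and venous SIRs elevated shortly after infection.

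If nearly everyone in a database is cut off before day 180, the early, higher-risk days make up too much of the person-time and the 180-day SIR is pushed up. The amount depends on the lock date. For cohort 2, databases with identical true risks would then report different 180-day SIRs, and I² would partly measure lock dates. Cohorts 3 and 4 rely on inpatient data held only in SIDIAP, so no other database can fill in their late follow-up.

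**Working it through.** The protocol gives no figure of its own to reproduce here.

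**Step 1: dates.** Table 1 dates are day/month/year, since the Estonian entry 31/3/2021 can be read no other way. From 1 December 2021 to 1 June 2022 is 31+31+28+31+30+31 = 182 days. The last index date with a complete window is the lock minus 180 days:

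| Database | Listed lock | Last index date for 180 days |
|---|---|---|
| SIDIAP | 1 Jun 2022 | 3 Dec 2021 |
| CPRD GOLD | 1-31 Jul 2022 (day not given) | 2 Jan to 1 Feb 2022 |
| IQVIA Germany | 1 Sep 2022 | 5 Mar 2022 |
| IPCI | 1 Dec 2022 | 4 Jun 2022 |

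If the index date counts as day 1, the SIDIAP date becomes 4 December. For 90 days the SIDIAP date is 3 March 2022.

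**Step 2: assumptions.** The protocol gives neither the entry pattern nor the risk profile. Two entry patterns were used: uniform from 1 December 2021 to the lock, and peaked in mid-January (normal shape, mean day 45, SD 25 days). Follow-up is F = min(180, lock − index). Deaths, outcomes and other losses are ignored. In SIDIAP, mean follow-up is about 92 days (uniform) or 135 days (peaked). The share able to complete 180 days is 1.6% or 1.0%.

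**Step 3: SIR.** For a rate ratio k in the first 30 days and 1 afterwards, SIR = 1 + (k − 1)p, where p is the share of person-time in the first 30 days. With complete follow-up p = 30/180 = 0.167, so k = 5 gives 1 + 4 × 0.167 = 1.67.

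| Database | p, peaked | SIR (k = 5) | p, uniform | SIR (k = 5) |
|---|---|---|---|---|
| SIDIAP | 0.222 | 1.89 | 0.302 | 2.21 |
| CPRD GOLD, 1 Jul | 0.186 | 1.74 | 0.269 | 2.08 |
| CPRD GOLD, 31 Jul | 0.170 | 1.68 | 0.249 | 2.00 |
| IQVIA Germany | 0.167 | 1.67 | 0.234 | 1.94 |
| IPCI | 0.167 | 1.67 | 0.212 | 1.85 |

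With k = 3 the complete-follow-up value is 1.33, and SIDIAP gives 1 + 2 × 0.222 = 1.44 to 1 + 2 × 0.302 = 1.60.

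**Step 4: a slower decline.** Take ratios of 5, 2 and 1 for days 0-30, 31-90 and 91-180. Complete follow-up gives (5×30 + 2×60 + 1×90)/180 = 2.00. SIDIAP gives 5×0.222 + 2×0.442 + 0.336 = 2.33 (peaked) and 5×0.302 + 2×0.441 + 0.257 = 2.65 (uniform). If entry is concentrated narrowly around 31 December, SIDIAP gives 2.19.

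**Step 5: the 90-day window.** With k = 5 and complete follow-up, p = 30/90 and the SIR is 2.33. In SIDIAP, peaked entry gives p = 0.334 and 2.34. Uniform entry gives p = 0.406 and 2.62.

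**The case against.** Several counter-arguments stand.

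- A reader might infer that the 180-day results cannot be delivered in SIDIAP, or that the protocol wrongly promises complete 180-day follow-up. Neither is supported. Section 8.4 makes 180 days a maximum and lets people contribute the time they have, so a rate and an SIR can be calculated.
- Table 1 gives the lock of the last update, not a committed analysis lock. Section 8.3 uses the last available data, section 5 leaves code execution to be confirmed, and the protocol version is dated October 2023. A later release could cure the problem. Still, the listed lock is the only one stated, and nothing commits to a refresh.
- Section 11 already concedes an effect on the 90- and 180-day rates, and section 8.8.1 will report time at risk, so truncation would be visible. But section 11 names CPRD rather than the database with the earlier listed lock, and sets no remedy.
- The bias depends on assumptions. Section 6 also cites venous risk raised to 49 weeks, and a rate ratio constant over 180 days would give no bias.
- It is tempting to extend the point to the 90-day SIR. Step 5 shows that effect is negligible unless entry is spread evenly.
- Cumulative incidence functions and Cox models handle censoring. However, cumulative incidence is planned at 90 days only, so no 180-day incidence measure in the protocol is robust to truncation.
- The pooling argument applies to cohort 2 only, because cohorts 3 and 4 depend on SIDIAP alone. Section 8.5 does not tie cohort 5 to 1 December 2021, so it is not affected in the same way.

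**Conclusion.** The point holds for cohorts 2 to 4 on the lock listed for SIDIAP. Only entries on 1-3 December 2021, about 1-2% under the assumed patterns, can complete 180 days. The 180-day rate and SIR are computable, but they over-weight early follow-up if risk declines after infection. In the k = 5 example the SIDIAP SIR is inflated from 1.67 to between 1.89 (13%) and 2.21 (32%). For cohort 2 the result is not comparable with later-lock databases before pooling. The dates are exact. The size is illustrative, since entry pattern and risk decline are assumed, and a later SIDIAP release would shrink or remove the effect. It is worth correcting before code is run, because the 180-day window is written into objective 2 and feeds objective 5.

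**What to change.** - In sections 8.8.2 and 8.8.5, report rates and SIRs in disjoint bands (0-30, 31-60, 61-90 and 91-180 days). This keeps every entry. Build any 180-day summary from the bands with fixed weights common to all databases.
- Alternatively, limit each window to entries indexed on or before the lock minus the window. On the listed lock this would discard about 98-99% of SIDIAP entries from the 180-day analysis, so the bands are preferable.
- In section 8.9, do not pool a cumulative 180-day SIR from a database whose lock does not support that window.
- State which windows each database supports at the actual extraction date.
- In section 11, name SIDIAP as having the earliest listed lock of the databases used for objectives 2 to 5.

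The cost is protocol wording and a change to how person-time is split. The downside is wider intervals in the late bands, and little SIDIAP information near day 180 on the current lock.

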Main measure of effect:	The incidence of each study outcome will be estimated during 30-, 60-, and 90- and 180-days following the index date for the general pre-pandemic population cohort, the people with COVID-19 cohort, and the vaccinated cohort with 95% confidence intervals. The 90-day cumulative incidence of study outcomes will be estimated. Incidence rate ratios will be calculated.

B. Secondary research question and objective

Outcome:	
For the secondary analysis, we will be looking at the outcomes in the primary analysis separately, with additional outcome events as well. All other contents in the table are the same as the primary.
 
 1. Venous thromboembolic events 
In a secondary analysis pulmonary embolism and deep vein thrombosis will be assessed separately. We will also assess portal vein thrombosis, splanchnic venous thrombosis (SVT) and cerebral venous sinus thrombosis separately.
 2. Arterial thromboembolic events 
In a secondary analysis acute myocardial infarction and acute ischemic stroke will be assessed separately. We also identify stroke in general, for which we will include both ischemic, haemorrhagic and non-specifically recorded stroke.
 3. Cardiovascular events 
Instances of heart failure, cardiac arrhythmia, and angina will be identified. In addition, major cardiovascular events (MACE) will be identified by heart failure, acute myocardial infarction, or stroke, or the occurrence of sudden cardiac death. As a sensitivity analysis, we will require that events were identified by hospitalisation admission or discharge records.

-----------------	--

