Measurement characteristics/validation: If there are measurement characteristics for the outcome algorithm (e.g. PPV, sensitivity, specificity) from publications, or from outcome validation within the study population (e.g., medical record review), provide this information.

Source of algorithm: Specify the source of algorithms to define the time 0 or primary anchor criteria.

The table below further describes the operational definitions with regard to the follow-up start and the follow-up end.

Follow up start	Day 1	Index date
Follow up end¹	Select all that apply	Specify
Date of outcome	Yes	
Date of death	Yes	
End of observation in data	Yes	

	Phase II C3-001 – Study Protocol	
	Author(s): [name], [name]	Version: v3.1
	Dissemination level: public	

Day X following index date (specify day)	Yes	180 days after index date
End of study period (specify date)	Yes	End of data availability per database
End of exposure (specify operational details, e.g. stockpiling algorithm, grace period)	n/a	
Date of add to/switch from exposure (specify algorithm)	n/a	
Other date (specify)	n/a	

¹ Follow up ends at the first occurrence of any of the selected criteria that end follow up.

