 - whether the vaccination record is 1st, 2nd, 3rd or 4th dose. A 21 day gap between two consecutive records of vaccine will be required to avoid repeated records of the same vaccine. The 21-days period was chosen based on the minimal recommended dosing schedule of the primary vaccine course in participated databases (Spain).
 - have at least 365 days of data availability prior to index date

Cohorts 2 to 5 will be stratified by prior COVID-19 infection status and for cohorts 2 to 4 also by prior SARS-CoV-2 vaccination status. All cohorts will additionally be stratified by whether patients are immunocompromised on the index date. People in each of the five cohorts will be required to have at least a year of observed history in the database prior to their index date. This is to ensure a sufficient time period to identify health conditions and medication use prior to individuals' index dates.

	Phase II C3-001 – Study Protocol	
	Author(s): [name], [name]	Version: v3.1
		Dissemination level: public

Table 3. Operational Definitions of Inclusion Criteria

Criterion	Details	Order of application	Assessment window	Care Setting ¹	Code Type	Diagnosis position ²	Applied to study populations:	Measurement characteristics/validation	Source for algorithm
Observation period of 365day prior entry (all 5 cohorts)	Study participants will be required to have 365 days prior history observed before contributing observation time	before	[-365,0]	n/a	n/a	n/a	All individuals within the selected databases	n/a	n/a
Covid-19 infection (cohort 2)	have either a positive test result for SARS-CoV-2 or a clinical diagnosis of COVID-19 on or after 1 st December 2021 (with the index date being whichever date comes first if both occur)	before	n/a	Primary care	SNOMED	n/a	All individuals within the selected databases	n/a	n/a
Covid-19 hospitalized (cohort 3)	a hospitalisation on or after 1 st December 2021 (with the index date the date of hospital admission), a record of a clinical diagnosis of COVID-19 or a positive test result for SARS-CoV-2 in the period between 3 weeks prior to and up to 3 days following the index date	before	[-21, 3]	Primary care, secondary care	SNOMED	n/a	All individuals within the selected databases	n/a	n/a

	Phase II C3-001 – Study Protocol	
	Author(s): [name], [name]	Version: v3.1
	Dissemination level: public	

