deep vein thrombosis		No	Binary, time-to-event	[-183,-1]	IP,OP	SNOMED	n/a	All included cohorts	n/a	n/a
portal vein thrombosis		No	Binary, time-to-event	[-183,-1]	IP,OP	SNOMED	n/a	All included cohorts	n/a	n/a
splanchnic venous		No	Binary, time-to-event	[-183,-1]	IP,OP	SNOMED	n/a	All included cohorts	n/a	n/a

	Phase II C3-001 – Study Protocol	
	Author(s): [name], [name]	Version: v3.1
	Dissemination level: public	

thrombosis (SVT)										
cerebral venous sinus thrombosis		No	Binary, time-to-event	[-183,-1]	IP,OP	SNOMED	n/a	All included cohorts	n/a	n/a
acute myocardial infarction		No	Binary, time-to-event	[-183,-1]	IP,OP	SNOMED	n/a	All included cohorts	n/a	n/a
acute ischemic stroke		No	Binary, time-to-event	[-183,-1]	IP,OP	SNOMED	n/a	All included cohorts	n/a	n/a
stroke in general	stroke in general will include both ischemic, haemorrhagic and non-specifically recorded stroke.	No	Binary, time-to-event	[-183,-1]	IP,OP	SNOMED	n/a	All included cohorts	n/a	n/a

¹ IP = inpatient, OP = outpatient, ED = emergency department, OT = other, n/a = not applicable

² Specify whether a diagnosis code is required to be in the primary position (main reason for encounter)

8.6.3. Other covariates, including confounders, effect modifiers and other variables (where relevant)

Location at index date

For cohort 2 (Persons tested positive for SARS-CoV-2 or with a clinical diagnosis of COVID-19) and cohort 5 (Persons vaccinated against SARS-CoV2 infection) we will identify whether individuals were currently hospitalised on their index date. All people in the cohort 3 (Persons hospitalised with COVID-19) and cohort 4 (Persons requiring intensive services during a hospitalisation with COVID-19) will be hospitalised on their index date.

Demographics

Patients' age at index date and sex will be identified. Age groups will also be identified using the following groupings: <20; 20-44; 45-54; 55-64; 65-74; 75-84; ≥85 years. For those databases where such information is available, individual or area level socioeconomic status and whether they are living in the community or were a nursing home resident will also be identified.

Health conditions pre-index date

Individuals' history of the study outcomes will be identified over three time periods prior to the index date:

- 1) 30 days prior to one day prior index date,
- 2) 365 days prior to one day prior index date,
- 3) all available days observed up to one day prior to index date.

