		Dissemination level: public

We will calculate crude incidence rate ratios (IRRs) for each event with 95% confidence intervals, for the vaccinated and COVID-19 cohorts compared against the background general population cohort. This will be done both overall and stratified by key factors including age, sex, prior COVID-19 diagnosis, prior vaccination status and whether patients are immunosuppressed. We will estimate the number of events expected among the vaccinated and COVID-19 cohorts using indirect standardisation by age and sex (with 10-year age bands), using the general population cohort as the standard population. We will calculate standardized incidence rate ratios (SIRs) and 95% confidence intervals comparing observed and expected rates. Rates will be reported overall, and by 10-year age bands, by sex, by prior COVID-19 diagnosis, by prior vaccination status and whether patients were immunosuppressed. A standardized incidence rate ratio above 1 will indicate that the observed rate for a specific outcome is higher than what is expected in the general background population.

Table 8: Primary, secondary, and subgroup analysis specification

A. Primary analysis

Hypothesis:	Objective 1 -3: Not applicable, descriptive incidence rate. Objective 4: use of intensive care services during a hospitalisation can be considered as key intermediate events between testing positive for SARS-COV-2 or having a clinical diagnosis of COVID-19 in an outpatient setting on the one end to a COVID-19-related death on the other. Objective 5: Covid-19 infection or vaccination may change the incidence rate of study events in population.
Exposure contrast:	Objective 1 -3: Not applicable, descriptive incidence rate. Objective 4: Not applicable, risk factor analysis Objective 5: Infected or vaccinated vs. the non-infected or non-vaccinated population
Outcome:	Objective 1 -3: Incidence rates of VTE, ATE Objective 4: VTE, ATE, death Objective 5: Incidence rates of VTE, ATE
Analytic software:	R

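### SIRs by immunosuppression take expected counts from the whole general population, and background time at risk is defined in two incompatible ways

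*Protocol*

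**What the plan says.** **Expected counts.** Section 8.8.5 obtains expected events "using indirect standardisation by age and sex (with 10-year age bands), using the general population cohort as the standard population". Table 8 (objective 5) repeats this, and section 11 confirms that standardised rates allow for age and sex alone. The reporting sentence in 8.8.5 reads: "Rates will be reported overall, and by 10-year age bands, by sex, by prior COVID-19 diagnosis, by prior vaccination status and whether patients were immunosuppressed". The subgroup row of Table 8 adds that all analyses are stratified by immunocompromised status where numbers allow.

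**Immune status in the background.** Section 8.5 states: "All cohorts will additionally be stratified by whether patients are immunocompromised on the index date". That includes cohort 1, the pre-pandemic background. For objectives 1-3, Table 8 also plans rates by immune status within age-sex strata. Section 8.6.3 defines the group by HIV/AIDS, haematological or solid malignancy, other intrinsic immune conditions, antineoplastic or immunomodulating treatment, or corticosteroids combined with transplantation or inflammatory disease.

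**Background time at risk.** Section 8.4 says: "For cohort 1, follow-up will begin on January 1st 2017 and continue up until the first of" a list that closes with 31 December 2019. It gives the day limits only to cohorts 2 to 5. Section 8.5 and the population and time rows of Table X agree. But the main-measure row of the same Table X plans incidence over 30, 60, 90 and 180 days "following the index date for the general pre-pandemic population cohort". Section 8.8.2 applies those windows to each cohort of interest, and the follow-up end table in 8.4 stops at "180 days after index date" with no exception for cohort 1.

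**The concern.** Objective 5 sets the infected and vaccinated cohorts against the background, and Table 8 names the SIR as the confounding adjustment for rate ratios. Malignancy and its treatment are part of the immunocompromised definition, so this stratum can be expected to have a higher thromboembolic rate whatever its exposure. An SIR above 1 there could then appear with no effect of infection or vaccination. Since the protocol already plans background rates by immune status, this is a mismatch between two parts of the plan and not a limit of the data.

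The second conflict concerns the denominator behind every expected count and every crude rate ratio. Two programmers following different sections would produce different background rates, from different calendar periods, for the same study.

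**Working it through.** The protocol states no rate, event count, prevalence or precision target, so there is no planned figure to reproduce.

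**1. SIR with no exposure effect in the immunosuppressed stratum**

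Inputs, both assumed:
- p, the immunosuppressed share of the background: 3-10%.
- r, the event rate in immunosuppressed relative to other people: 1.5-3.

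Let the rate in people who are not immunosuppressed be 1 within an age-sex cell. The whole-population rate in the cell is then 1 - p + p·r. With no exposure effect, immunosuppressed people in the exposed cohort have rate r, so

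null SIR = r / (1 - p + p·r), and in the remaining people 1 / (1 - p + p·r).

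If p and r are the same in every cell, this holds for any age-sex mix.

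| r | p | Denominator | Null SIR, immunosuppressed | Null SIR, others |
|---|---|---|---|---|
| 1.5 | 3% | 1.015 | 1.48 | 0.985 |
| 1.5 | 10% | 1.05 | 1.43 | 0.952 |
| 2 | 3% | 1.03 | 1.94 | 0.971 |
| 2 | 10% | 1.10 | 1.82 | 0.909 |
| 3 | 3% | 1.06 | 2.83 | 0.943 |
| 3 | 10% | 1.20 | 2.50 | 0.833 |

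With expected counts from the same immune-status stratum, the null SIR would be 1.00 in both groups.

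**2. Background time at risk for a person entering on 1 January 2017**

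- To 31 December 2019: 3 × 365 = 1,095 days.
- 30-day window: 30 / 1,095 = 2.7% of that time, ending about 31 January 2017; 1,095 / 30 = 36.5-fold less.
- 180-day window: 180 / 1,095 = 16.4%, ending about 30 June 2017; 1,095 / 180 = 6.1-fold less.

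Everyone who already has 365 days of history enters on 1 January 2017. Under the short windows most background time would therefore fall in January, or in January to June, of that one year. People who reach 365 days later would enter later.

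As an upper-bound illustration, take the 5.8 million active subjects that Table 1 gives for SIDIAP. Full follow-up gives 5.8 × 1,095 / 365.25 = 17.4 million person-years. The 30-day window gives 5.8 × 30 / 365.25 = 0.48 million, and the 180-day window 2.86 million.

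**The case against.** **On immune status.** The reporting sentence in 8.8.5 has rates as its subject, not SIRs. The crude rate ratio is expressly stratified by immune status and may use matched background rates. Section 11 discloses that standardisation covers age and sex only and that strata will be inspected. Section 8.8.5 reads an SIR above 1 only as higher than expected in the general background population. This narrows the point to the SIR, and it means the protocol does not itself claim an exposure effect. It does not remove the point: the sentence follows directly on the SIR definition, Table 8 stratifies all analyses by immune status, and no text says that the stratum's expected counts come from matching background rates.

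**On time at risk.** Every follow-up rule written specifically for cohort 1 runs to the end of 2019, and the objectives attach day windows only to the COVID-19 and vaccinated cohorts. The follow-up end table may be a generic one for cohorts 2 to 5. That stands. A reader might infer that a January-only background is the planned result, or that every SIR is therefore shifted. The documents support neither; it is what one of two conflicting readings would produce.

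**On age.** A reader might also infer that background people stay in their entry age band for up to three years, because section 8.6.3 says that "age at index date and sex will be identified". That sentence only lists a covariate. Nothing in the protocol says whether background person-time moves between bands as people age, and a statistical analysis plan may settle it. Any such drift would also nearly vanish under the short windows. No finding is made on it.

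**Conclusion.** Both parts hold in limited form.

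As written, the SIR by immunosuppressed status does not compare like with like. With no exposure effect it would be about 1.4-2.8 in immunosuppressed people and about 0.83-0.99 in the rest, given an assumed prevalence of 3-10% and an assumed rate ratio of 1.5-3. No figure in the protocol supports particular values, so these sizes are illustrative. The direction needs only that immunosuppressed people have the higher underlying rate. The finding does not extend to the crude rate ratio.

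Background time at risk is contradicted within the protocol, and even within Table X: up to 1,095 days against 30-180 for a person entering on 1 January 2017. The weight of the text favours the full period. The effect of the short windows on the SIRs cannot be sized from the documents.

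Both should be corrected before the analysis code is fixed.

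**What to change.** - **Section 8.8.5 and Table 8:** state that, for SIRs by immunosuppressed status, expected counts come from background age-by-sex rates in the same immune-status stratum, which section 8.5 and Table 8 already provide for.
- **Background immune status:** re-assess it during 2017-2019, for example at each 1 January, with the look-back periods of section 8.6.3. If it is fixed at entry, the status would be up to three years old by the end of follow-up and the match would be poor.
- **Background time at risk:** state once that the rates feeding the crude rate ratios and SIRs use person-time from 1 January 2017, or from the date on which 365 days of history is reached, to 31 December 2019. Exempt cohort 1 from the day windows in the main-measure row of Table X, the follow-up end table in 8.4, and section 8.8.2.

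The cost is a few sentences and a little more coding, with no new data. Age-by-sex-by-immune-status cells will be sparser, so expected counts for rare outcomes will be less stable.
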